8.10 Other Aspects

8.10.1 Scientific Advisory Committee

A SAC will act in an advisory capacity to the Sponsor to provide guidance to the study design, conduct, analysis methodology and to support its successful completion. The Scientific Advisory Committee will focus on evaluating emerging evidence, providing “report to stakeholders”, “public data lens” and making recommendations including:

- Strategies to optimize data collection, recruitment of HCW populations and potential real-world prophylactic therapies.
- Signals to escalate (association, safety, sub-population issues).

8.10.2 Transparency

To facilitate updates on study progress, SAC endorsed summary level and de-identified data evolving from the progress of the UNITY Global Registry will be communicated intermittently on COVIDpharmacology.com.

9 PROTECTION OF HUMAN SUBJECTS

9.1 Good Pharmacoepidemiology Practices

The procedures set out in this study protocol are designed to ensure that the Sponsor and Study Lead abide by the principles of the International Society for Pharmacoepidemiology GPP guidelines.¹¹ The study also will be carried out in keeping with local legal requirements.

9.2 Electronic Informed Consent

Before each participant is admitted to the study, informed consent will be obtained electronically from the HCW according to the regulatory and legal requirements of the participating country (in parallel, paper consents may be required in certain countries, e.g.,: Uganda and Zimbabwe according to local regulations.). Record of this consent will be retained in the study database (or country specific binders which will be archived at site according to local regulations).

If a protocol amendment is required, the informed consent form may need to be revised to reflect the changes to the protocol. If the consent form is revised, it must be reviewed and approved by the appropriate Institutional Review Board/Independent Ethics Committee (IRB/IEC), and signed by all participants subsequently enrolled in the study as well as those currently enrolled in the study.

9.3 Protocol Approval and Amendment

Before the start of the study, the study protocol and/or other relevant documents will be approved by the IRB/IEC/Competent Authorities, in accordance with local legal requirements. The Sponsor must ensure that all ethical and legal requirements have been met before the first participant is enrolled in the study.

To alter the protocol, amendments must be written, receive approval from the appropriate personnel, and receive IRB/IEC/Competent Authority approval prior to implementation (if appropriate).

Administrative changes (not affecting participant risk) may be made without the need for a formal amendment. All amendments will be distributed to all protocol recipients, with appropriate instructions.

9.4 Confidentiality

All study findings and documents will be regarded as confidential. The Study Lead and members of his/her research team must not disclose such information without prior written approval from the Sponsor.

The anonymity of participants must be maintained. Study Leads shall ensure that personal identifiers will be removed from any study files that are accessible to non-study personnel in accordance with applicable laws and regulations. Participants will be identified in documents submitted to Parexel by their identification number, initials and/or birth date,

not by name. Documents not to be submitted to Parexel that identify the participant (e.g., the signed informed consent) must be maintained in confidence by the Study Lead.

9.5 Duration of the Study

The registry will remain open in different regions of the world for as long as the pandemic continues regionally.

For an individual participant, the maximum duration of participation in the study will be up to 12 weeks.

The entire study will end 12 weeks after the last-participant-in date.

9.6 Premature Termination of the Study

The study may be terminated early at the Sponsor's discretion. Conditions that may warrant termination include:

- Failure to enroll participants at an acceptable rate.
- A decision on the part of the Sponsor to suspend the study for administrative reasons.
- Ethical reasons.

10 MANAGEMENT AND REPORTING OF ADVERSE EVENTS/ADVERSE REACTIONS

No AEs/adverse reactions will be collected during this study.

There are no physical risks to the participants in the study given the observational nature of the study design, apart from the minimal risk for obtaining blood/serology for SARS-COV-2 testing. A key risk to participants is a potential breach of confidentiality of the medical record information and the associated privacy. However, this risk is mitigated due to the data privacy measures incorporated in the web application system to key code participant data on the central reporting database accessible by the study team for data analysis.

If any unanticipated problems related to the study involving risks to participants or others happen during the course of this study, these will be reported to the IRB/IEC in accordance with all applicable IRB/IEC, local, and regulatory requirements. Any participant who believes that a serious risk may be associated with exposure to any prophylactic/concomitant treatment during the course of this study must report the AE to the manufacturer of the treatment, in accordance with applicable regulatory requirements.

Unanticipated problems that do not involve risks to participants or others will be summarized in narrative or other format and submitted to the IRB/IEC at the time of continuing review, if required.

11 PLANS FOR DISSEMINATING AND COMMUNICATING STUDY RESULTS

Near real-time descriptive analytics dashboard will be made available in a continuous manner to provide a high-level view of pre-defined study variables/data. Additionally, emerging data on COVID-19 will be publicly shared, as appropriate.

The study findings may be disseminated if they are found to be of scientific or public health importance. Study results may be included in abstracts sent to scientific congresses. Specific plans for disseminating and communicating the study results will be produced when the results are available.

Appendix 1: WHO Ordinal Scale for Clinical Improvement ⁹

Patient State	Descriptor	Score
Uninfected	No clinical or virological evidence of infection	0
Ambulatory	No limitation of activities	1
	Limitation of activities	2
Hospitalized Mild disease	Hospitalized, no oxygen therapy	3
	Oxygen by mask or nasal prongs	4
Hospitalized Severe Disease	Non-invasive ventilation or high-flow oxygen	5
	Intubation and mechanical ventilation	6
	Ventilation + additional organ support – pressors, RRT, ECMO	7
Dead	Death	8

Note: This scale has been used as a basis and adapted for the abbreviated version being employed in this study.

Appendix 2: Detailed SoA

Variable domain	At Enrollment	Weekly follow-up (until Week 12)	
		HCW	HCW Contact
Inclusion/eligibility criteria			
Screening questions	X	-	-
Index date (date of first COVID-19 exposure)	X	X	-
Electronic/Paper (if applicable) consent			
	X	-	-
Demographics			
Contact information	X	-	-
Secondary contact	X	-	-
Facility	X	-	-
Date of birth (Age)	X	-	-
Gender	X	-	-
Weight	X	-	-
Height	X	-	-
Race	X	-	-
Blood type	X	-	-
Smoking status (current/past/never smoked)	X	-	-
BCG vaccination history (date, time period)	X	-	-
WHO Ordinal Scale for Clinical Improvement of COVID-19 (adapted, abbreviated version)			
SARS-CoV-2 (uninfected/ infected)	X	X	X
Ambulatory status (limitation/no limitation of activities)	X	X	X
Hospitalized with no ICU or mechanical ventilation (mild)	X	X	X
Hospitalized with ICU or mechanical ventilation (severe)	X	X	X
Death	-	-	X
Prophylactic treatments (treatment exposure)			
Treatment name	X	X	-
Date started	X	X	-
Date stopped	X	X	-
Dose (intake)	X	X	-
Duration of treatment	X	X	-
Dose frequency and dosing interval	X	X	-
Status (stopped/ongoing)	X	X	-
Reason for stopping (not available/side effects/ expense/other)	X	X	-
Number of missed doses (yes/no)	X	X	-
If yes, reason? (not available/side effects/expense/other)	X	X	-
History of exposure to COVID-19 patients			
Self-reported ongoing and recurrent exposure (yes/no)	X	X	-
WHO exposure definition (3 questions) (yes/no)	X	X	-
Direct care to COVID-19 patient (yes/no)	X	X	-
Face-to-face contact (yes/no)	X	X	-
Present during aerosol-generating procedures (yes/no)	X	X	-
Days worked past week	-	X	-
Number of COVID-19 cases exposed to in the past week	-	X	-
Personal Protective Equipment			
Mask (N95 respirator mask or other) (if yes, always/not always)	X	X	-
Eye protection/goggles/face shield (if yes, always/not always)	X	X	-
Gown (if yes, always/not always)	X	X	-
Gloves (if yes, always/not always)	X	X	-
If “not always” or “no” for mask:			

Number of COVID-19 cases exposed to in the absence of a mask in the prior week	-	X	-
Longest COVID-19 exposure in the absence of a mask	-	X	-
COVID-19 symptoms			
Develop symptoms (yes/no), if yes – date the symptoms begin:	X	X	-
Fever (temperature over 38°C)	X	X	-
Subjective fever (felt feverish)	X	X	-
Chills	X	X	-
Myalgia (muscles hurt or ache)	X	X	-
Rhinorrhea (runny or drippy nose)	X	X	-
Pharyngitis (sore throat)	X	X	-
Cough (new onset or worsening of chronic cough)	X	X	-
Dyspnea (hard to breathe or difficulty breathing)	X	X	-
Pneumonia	X	X	-
Nausea or vomiting	X	X	-
Headache or migraine	X	X	-
Abdominal pain (pain in tummy)	X	X	-
Asthenia (weakness or loss of strength)	X	X	-
Arthralgia (joint pain)	X	X	-
Anosmia (loss of smell)	X	X	-
Ageusia (loss of taste)	X	X	-
Blue coloring in toes	X	X	-
Diarrhea (two or more looser-than-normal stools in 24 hours)	X	X	-
SARS-CoV-2 testing			
Tested? (yes/no)	X	X	-
Type of test	X	X	-
PCR (positive/negative)	X	X	-
Antigen test (positive/negative)	X	X	-
Serology (IgG and/ or IgM, positive/negative or titer)	X	X	-
Date of test	X	X	-
Serology testing	X	X	-
Household history (COVID-19)			
Number of household contacts	X	X	-
Additional household member(s) exposed to COVID-19 (yes/no) If yes, how many?	X	X	-
Additional household member(s) with symptoms consistent with COVID-19 (yes/no) If yes, how many?	X	X	-
Additional household member(s) diagnosed with COVID-19 (yes/no) If yes, how many?	X	X	-
Underlying conditions and key morbidities			
Chronic lung disease	X	-	-
Diabetes mellitus	X	-	-
Cardiovascular (heart) disease	X	-	-
Chronic renal (kidney) disease	X	-	-
Chronic liver disease	X	-	-
Immunocompromised condition (HIV/AIDS, organ transplant, other)	X	-	-
Tuberculosis	X	-	-
Neurologic/neurodevelopmental	X	-	-
Hypertension (high blood pressure)	X	-	-
History of stroke	X	-	-
Other chronic diseases	X	-	-
If female, currently pregnant	X	-	-
If female, currently breastfeeding/lactating	X	-	-
Job characteristics			
Type of healthcare work	X	-	-

Primary work location (ED, ICU, Medical floor)	X	X	-
Number of hours with patients	X	X	-
Concomitant medications (other than for COVID-19)			
Antibiotics (yes/no)	X	X	-
Antimalarials (yes/no)	X	X	-
Antiparasitics (yes/no)	X	X	-
Antiretrovirals for HIV (yes/no)	X	X	-
Antivirals (yes/no)	X	X	-
Medication for high blood pressure and cardiovascular disease (yes/no)	X	X	-
Nonsteroidal Anti-inflammatory Drugs (NSAIDs) (yes/no)	X	X	-
Botanicals (yes/no)	X	X	-
Immunocompromising drugs (yes/no)	X	X	-
COVID-19 vaccine (to be selected as applicable)			
Convidicea (Ad5-nCoV)	X	X	
CoronaVac (Sinovac)	X	X	
Covaxin (BBV152)	X	X	
EpiVacCorona (Vector Institute)	X	X	
Janssen Pharmaceuticals (Johnson & Johnson) (Ad26.COV2.S)	X	X	
Moderna COVID-19 Vaccine	X	X	
Novavax (NVX-CoV2373)	X	X	
Oxford-AstraZeneca COVID-19 Vaccine	X	X	
Pfizer-BioNTech COVID-19 Vaccine	X	X	
Sinopharm BBIBP-CorV	X	X	
Sputnik V COVID-19 Vaccine	X	X	
Other (please specify)	X	X	

Appendix 3: List of Prophylactic Treatments

Select ALL that apply

1. Chloroquine - specify dose and interval
2. Hydroxychloroquine - specify dose and interval
3. Azithromycin - specify dose and interval
4. Lopinavir/ritonavir - specify dose and interval
5. Ivermectin - specify dose and interval
6. Other 1 – specify therapeutic, dose and interval
7. Other 2 – specify therapeutic, dose and interval
8. Other 3 – specify therapeutic, dose and interval

Signature Page for VV-TMF-757477 v0.1

Reason for signing: Approved	Name: [name] Role: Sponsor Date of signature: 17-Jun-2021 16:41:02 GMT+0000
------------------------------	---

Signature Page for VV-TMF-757477 v0.1

6.1 Overview.....	17
6.2 Missing values.....	18
6.2.1 Missing values for non-outcome variables	18
6.2.2 Missing values for outcomes.....	18
6.3 Descriptive analyses.....	18

6.3.1	Facility characteristics.....	19
6.3.2	Demographic characteristics.....	19
6.3.3	Household characteristics.....	20
6.3.4	Exposure to COVID-19 patients.....	20
6.3.5	Medical history.....	21
6.3.6	Medications for non-COVID-19 related purposes.....	22
6.3.7	Prophylactic medications.....	23
6.3.8	PPE usage	24
6.3.9	COVID-19 symptoms.....	25
6.4	Primary analysis	26
6.4.1	Frailty model: mixed effect Cox regression	26
	Table 5.4.1.....	26
6.5	Secondary analysis	27
6.6	Subgroup analyses	28
6.7	Sensitivity analyses	28
7	Minimization of study bias.....	30
7.1	Selection bias	30
7.2	Survival bias	30
7.3	Recall bias.....	30
7.4	Information bias.....	30
7.5	Indication bias.....	30
7.6	Protopathic bias	31
8	References	31
9	Appendix.....	32
9.1	Shell tables.....	33
	Table 8.2.1 COVID-19 exposure status among all screened healthcare workers.....	33
	Table 8.2.2 Primary and Secondary Outcomes at baseline and follow-up among the overall population	34
Table 8.2.3	Static Variables by COVID-19 indication	35
Table 8.2.4	Household characteristics at baseline by COVID-19 indication.....	37
Table 8.2.5	COVID-19 exposure at baseline by COVID-19 indication	39
Table 8.2.6	Comorbidities at baseline by COVID-19 indication.....	40

Table 8.2.7 Concomitant medications at baseline by COVID-19 indication.....	41
Table 8.2.8 Prophylaxis use.....	43
Table 8.2.9 PPE usage at baseline.....	44

1 Introduction

The purpose of this statistical analysis plan (SAP) is to provide an analytic framework for the study “International Registry of Healthcare Workers Exposed to COVID-19 Patients (UNITY Global)”. This SAP addresses the statistical analyses that will be carried out in support of the protocol objectives. This analysis plan is based on the protocol version 1.0 of the study dated 08 June 2020.

2 Objectives of the study

This is an international registry of HCWs exposed to SARS-CoV-2 while caring for confirmed or clinically diagnosed COVID-19 patients. The aim of this registry is to generate real-world evidence in HCWs to potentially inform recommendations and policies on prevention measures, including prophylactic use of potential drug therapies in HCWs.

2.1 Primary objective

- To assess the association of potential prophylactic treatments with reduced risk of COVID-19 (or SARS-CoV-2 infection) in HCWs caring for COVID-19 patients.

2.2 Secondary objectives

- To characterize the type of potential prophylactic treatments, by dose and duration, overall, and by country/region/site.
- To explore the key factors (for example, use of PPE, HCW and healthcare facility characteristics, underlying co-morbidities, household history and COVID-19 exposure) modifying the risk of COVID-19 among HCWs.

[figure not shown]
3 Study overview

3.1 Study design

The UNITY Global Registry is designed to collect data on healthcare workers exposed to SARS-CoV-2 using longitudinal serial surveys implemented through a web/mobile application-based technology to encourage participation and facilitate rapid responses during this pandemic. Countries and healthcare facilities were selected based on the availability of potential prophylactic treatments to prevent workplace infection from SARS-CoV-2. Individuals with workplace exposure to confirmed or clinically diagnosed COVID-19 patients prior to enrollment, or anticipated within 30 days after enrollment, are eligible to participate. COVID-19 exposure is defined as per WHO classification¹. The date of the HCW's first known exposure to a confirmed or clinically diagnosed case of COVID-19 is referred to as the "Index Date" (see Figure 1). Healthcare worker volunteers are ineligible if they had COVID-19 or symptoms highly suggestive of COVID-19 before the Index Date. However, at the time of enrollment, HCWs can be either SARS-CoV-2 positive (symptomatic or asymptomatic) or SARS-CoV-2 negative. Healthcare workers are identified for participation via a central contact at participating healthcare facilities and are directed to a website/mobile application allowing them to electronically consent and answer questions that help assess their eligibility to participate. Information on potential prophylactic treatments used by HCWs are also collected.

All eligible HCWs in the study facilities are asked to enter the data in the registry via electronic data collection form. Data is collected at entry to the registry, and then weekly until 12 weeks after enrollment, death or lost to follow-up, whichever is earlier. A secondary contact is identified to be contacted to confirm status of HCWs in case of non-response/ loss to follow-up. In case of conflicts, responses by HCWs take precedence. Serology results from the laboratory will be loaded into the Local Data Store and merged with HCW contact information based on the participant identification numbers. Notification of results may be made available to the HCWs via secure access.

This is an observational cohort study; therefore, no preventive interventions, visits or laboratory tests are mandated. Dosing and duration of potential prophylactic treatment is at the discretion of the institution and/or healthcare provider, in accordance with regular local practice. However, serology testing for SARS-CoV-2 antibodies are being offered to the first 50% of participating HCWs per country, at enrollment and at the last follow-up (i.e. at Week 12).

Figure 1: Healthcare Worker Flow – Study Schematic

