8.2.3 Healthcare Worker Enrollment

Healthcare workers from participating healthcare facilities and clinics will be recruited through a centralized effort within each facility/clinic. Healthcare workers who agree to participate will be directed to a website/mobile application allowing them to electronically consent (in parallel, paper consents may be used, as per local requirements) and confidentially complete questionnaires (the details and frequency of these questions are provided in [Section 8.1](#)).

Enrollment will be continuously monitored and potentially capped to ensure that the study proportionately enrolls HCWs according to country, type of HCW and status of prophylaxis. For example, the registry will enroll approximately 75% of HCWs on a potential prophylactic therapy.

This registry will remain open and will continue to enroll HCWs for as long as the pandemic continues regionally, or until otherwise determined by the Sponsor.

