8.7.2 Analysis Population

The total pooled study population from all facilities will form the primary population for analysis.

Subgroup, stratified, and sensitivity analyses will also be defined in the SAP.

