5 Determination of Sample Size

The targeted sample size of approximately 10,000 HCWs assumes that 20% of the study population are non-exposed to potential prophylactic treatments, with a baseline risk of SARS-CoV-2 infection in the study period of 10% (for unexposed: not treated with potential prophylactic treatment). A total of N=10,000 allows for 80% power to identify an effect size of Relative Risk = 0.78.

If these sample sizes are not reached with respect the study population being exposed/non-exposed to potential prophylactic treatments, the relative risk may be detected with lower power or it may not be statistically significant. However, the secondary objectives can still be examined.

6 Statistical analysis

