6.1 Overview

All statistical analyses will be conducted using R (version 1.3.1093), unless otherwise specified.

For all descriptive analyses, categorical variables will be summarized by number of observations and percentage (%). Percentages will be rounded to one decimal place and will be based on available observations (known values), unless otherwise specified. Continuous variables will be summarized using descriptive statistics (n, mean, with standard deviation; minimum, first quartile, median, third quartile,

and maximum). Outliers will be included in descriptions as part of presenting ranges and percentiles (25th and 75th). The mean and SD will be rounded to one decimal place.

All statistical tests will be two-sided and at 5% level of significance.

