6.4 Primary analysis

6.4.1 Frailty model: mixed effect Cox regression

For the time to COVID-19 infection outcome, both crude and adjusted hazards ratios will be estimated for time to COVID-19 infection with respect to prophylaxis use. The primary objective of this analysis is to assess the association between prophylactic treatments and the reduced risk of SARS-CoV-2 infection in HCWs caring for COVID-19 patients. A mixed effect Cox regression model (ie. frailty model) will be used to estimate adjusted hazard ratios. This method will allow the utilization of both the repeated measures gathered from each HCWs surveys, as well as the incorporation of time-varying covariates of interest such as PPE usage and COVID-19 exposure. Each subject will be included as a random effect. Both time-fixed and time-varying covariates will be included in the model. Covariates will be assessed using a univariate model, any covariates with a p-value less than 0.20 will be included in a multivariate model. A backward stepwise process will then be completed, where the covariates with largest p-value are removed one at a time until all covariates that remain are significant at the 0.10 level. The time-fixed covariates, healthcare facility and country will be included in the model regardless of their significance level. Including the healthcare facility and country covariates will make each healthcare worker's COVID-19 outcome conditionally independent on the background COVID-19 incidence occurring within each subject's healthcare facility and country. A list of additional covariates to be considered can be found in Table 5.4.1. For each subject in the control group, the index date (ie. time of first known exposure to COVID-19 patients) will be used as time zero. For HCWs that are treated with prophylaxis at any time their index date will be 7 days after initiation of treatment. Having an index date near treatment initiation will prevent the introduction of survivorship bias into the analysis.

Table 5.4.1 Model Covariates

Time-fixed/Time-varying Covariate	Covariate Name
Time-fixed Covariates	Healthcare facility, Country, Age, Biological Gender, BMI, Smoking status, Ethnicity, Blood type, Primary work location, Type of healthcare worker, Medical history

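### The primary Cox model takes in infections from before enrolment under two different time zeros, so an inert prophylactic can look protective

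*SAP*

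**What the plan says.** SAP 3.1 and protocol 8.1 allow enrolment after infection: "at the time of enrollment, HCWs can be either SARS-CoV-2 positive (symptomatic or asymptomatic) or SARS-CoV-2 negative". The exclusion in SAP 3.1.1.2 reaches only infection before first known contact with a COVID-19 patient, not infection between that contact and enrolment.

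Protocol 8.7.2 sets the population: "The total pooled study population from all facilities will form the primary population for analysis". SAP 6.4.1 sets two time zeros. Controls start at first known contact, which may precede enrolment. HCWs treated at any time start 7 days after initiation, which the SAP presents as protection against survivorship bias. No delayed entry at enrolment is mentioned. The model is chosen partly because it allows "incorporation of time-varying covariates of interest such as PPE usage and COVID-19 exposure", but the time-varying list in Table 5.4.1 does not include prophylaxis.

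Three places indicate that HCWs infected at entry are in this model:
- SAP 6.3.5 worries about dating their comorbidities for the primary analysis.
- Shell Table 8.2.2 shows the primary outcome at baseline and follow-up together, by prophylaxis use.
- SAP 6.6 separates HCWs by COVID-19 status at entry only as a subgroup analysis.

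Protocol 8.9 acknowledges recall bias in recently infected enrollees, and survival bias in either direction.

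**The concern.** Infections before enrolment differ from those seen in weekly follow-up. They are recalled, and they enter the data only if the HCW later enrols. Their PPE, patient-contact and household history is one coarse retrospective report rather than a weekly series.

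The two time zeros then treat these cases unequally. A HCW infected before starting prophylaxis, who then never starts, stays a control and contributes an event. A HCW who does start begins the clock event-free, and the untreated time before initiation is discarded rather than credited to the control side. Early events therefore collect among controls.

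The headline hazard ratio is meant to inform policy on prophylaxis. SAP 6.7 also attaches a rule to it: an estimate of 0.8 or less without significance leads to a Bayesian analysis using published local data. A spurious estimate could trigger that step.

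**Working it through.** **1. The plan's own power figure.** Inputs from SAP section 5: N = 10,000; it "assumes that 20% of the study population are non-exposed to potential prophylactic treatments"; control risk 10%; relative risk 0.78. SAP 6.1 gives the test: "All statistical tests will be two-sided and at 5% level of significance". The stated result is: "A total of N=10,000 allows for 80% power to identify an effect size of Relative Risk = 0.78".

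- Expected events: 2,000 × 0.10 + 8,000 × 0.078 = 200 + 624 = 824.
- Schoenfeld power, taking the hazard ratio as 0.78: Φ(|ln 0.78| × √(824 × 0.2 × 0.8) − 1.96) = Φ(0.2485 × 11.48 − 1.96) = Φ(0.893) = 81.4%.
- Events needed for 80%: (1.960 + 0.842)² / (0.16 × 0.2485²) ≈ 795, or about 9,650 HCWs.

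The stated 80% is reproduced to within 2 points. Two-proportion formulas give more (87.7% pooled).

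**2. The primary model with no drug effect.** The documents do not give the lag from first contact to enrolment, or say how infection affects starting prophylaxis. The following are assumptions:
- true hazard ratio 1, with 10% infection risk per 12 weeks;
- first contact uniform up to 30, 90 or 180 days before enrolment, then 12 weeks of follow-up;
- 80% intend to use prophylaxis, starting at a random time between first contact and enrolment, and do not start if already infected;
- no selective enrolment.

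| Analysis | 30 days | 90 days | 180 days |
|---|---|---|---|
| Share of events before enrolment | 16% | 36% | 54% |
| SAP 6.4.1 clocks, all events | 0.74 | 0.55 | 0.47 |
| Same cases, one clock from first contact, time-varying prophylaxis (range) | 0.99–1.00 | 0.99–1.00 | 0.99–1.00 |
| SAP 6.6 subgroup without COVID-19 at entry, SAP clocks | 1.15 | 1.37 | 1.67 |
| Uninfected at entry, at risk from enrolment, time-varying prophylaxis (range) | 0.98–1.01 | 0.98–1.01 | 0.98–1.01 |

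The second and third rows differ only in clock and exposure coding. The bias is therefore the time-zero rule acting on cases from before enrolment, not pooling alone.

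The subgroup errs upward because its controls are credited with the time from first contact to enrolment, when by selection they could not have had an event. If starts can fall at any time, the subgroup ranged from 0.44 to 1.85 across the settings tried.

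**3. Sensitivity to behaviour after infection.** A second set of runs used mean lags of 15, 30 and 60 days, with 10% risk over the mean lag plus 12 weeks.
- If nobody starts after infection: 0.75, 0.63, 0.51.
- If half of the intended users infected first still start: 0.85, 0.78, 0.67.
- If all of them still start: about 1.01. They count as treated, and their infection falls before their time zero, so it drops out.

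**4. Selective enrolment alone.** With one clock, time-varying prophylaxis and the same lags:
- previously infected users half as likely to enrol: 0.92, 0.86, 0.84;
- previously infected non-users half as likely: 1.14, 1.26, 1.41.

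Correcting the clock while keeping cases from before enrolment would leave this bias, in either direction.

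**5. Changing the clock without the exposure coding.** If the clock starts at enrolment but the treated-at-any-time grouping stays, and half of starts fall in follow-up (an assumption), the null hazard ratio is about 0.38.

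**6. Power on events after enrolment only.** Scale the 824 events by the post-enrolment share from step 2:
- 84%: 692 events, Φ(0.2485 × √(692 × 0.16) − 1.96) = 74%.
- 64%: 527 events, 63%.
- 46%: 379 events, 49%.

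**The case against.** No sentence says that infections before enrolment are primary events. The pooling in protocol 8.7.2 is across facilities, and protocol 8.7.4 leaves the assignment of outcomes to exposure time to rules agreed with the advisory committee. That is fair: the conclusion comes from reading several sections together. If the sponsor intends otherwise, the SAP should say so.

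The biases are also partly disclosed. Protocol 8.9 names them, SAP 6.6 splits by entry status and by lag to enrolment, and SAP 7.1 to 7.3 compare with facility data. None of this changes the primary estimate.

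A reader might infer four stronger things that the documents or the check do not support:
- *Pooling by itself produces the protective figures.* It does not; one clock with time-varying prophylaxis returns about 1.0 when enrolment is not selective.
- *The unbiased analysis already exists in SAP 6.6.* It does not; that subgroup replicates the adjusted analysis on the same clocks.
- *The model cannot be fitted before enrolment.* The entry survey collects earlier PPE use, contact and household history, and dated prophylaxis starts and stops. The history is coarse and recalled, not absent.
- *Enrolment by prophylaxis status adds a bias of known size.* Enrolment is only "potentially capped to ensure that the study proportionately enrolls HCWs according to country, type of HCW and status of prophylaxis", and all eligible HCWs are to be offered entry (protocol 8.9). Nothing in the documents supports a figure.

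**Conclusion.** The concern holds. Followed as written, the plan places infections from between first contact and enrolment in the primary Cox model under unequal time zeros, and the resulting hazard ratio can be biased. With no true effect it can reach about 0.74, 0.55 or 0.47 for maximum lags of 30, 90 or 180 days, which is beyond the planning effect of 0.78.

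Those sizes rest on the assumed lags and on nobody starting prophylaxis after infection. They shrink if some infected HCWs still start and vanish if all do. The direction is not certain: selective enrolment can push the estimate either way, as protocol 8.9 says. The case for change is that the primary estimate depends on quantities the documents do not give, and that a change of text removes the dependence.

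**What to change.** In SAP 6.4.1 and protocol 8.7.2, define the primary analysis as HCWs without COVID-19 at or before entry, at risk from enrolment, or from first known contact if later. Code prophylaxis as a time-varying exposure, replacing the treated-at-any-time grouping and its separate time zero. If a 7-day lag is wanted, it can be built into that indicator. All three parts are needed: restriction alone leaves the subgroup bias of step 2, a corrected clock alone leaves selective enrolment (step 4), and an enrolment clock with ever-treated status gives step 5.

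Report infections at or before entry separately. Keep the pooled analysis as a sensitivity analysis, and use the same clock and exposure coding in the SAP 6.6 subgroups.

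No new data are needed. The cost is that events before enrolment leave the primary analysis. SAP section 5 assumes a "baseline risk of SARS-CoV-2 infection in the study period of 10" per cent, but SAP 3.2 uses study period for how long the registry stays open, while SAP 3.4 defines the 12-week follow-up separately. The sponsor should say which is meant. If it is the 12 weeks, nothing is lost. If earlier infections were included, restate power for 0.78: about 74%, 63% or 49% under the shares in step 6, against 81% with all events.
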